**CONFIDENTIAL**

Date: 17 December 2020  
 Version: 4.0  
 Status: Final  
 Page: 42 of 110

**Novo Nordisk**

### **Infant health information collected**

The following information will be collected for the infant:

- Details on the pregnancy outcome including:
  - Birth date
  - Gender
  - Gestational age (completed gestational weeks and days)
  - Head circumference of the newborna
  - Length of the newborna
  - APGAR scores assessed at 1 minute and 5 minutes after birth

a Measured in centimetres (cm) to one decimal place

- Standard Deviation (SD) score for birth weight (measured in grams (g) according to local normal curves for gestational age and sex) including the birth weight percentile.
- Details on the infant health status, including if the infant has any congenital anomaly or birth injury observed at gross examination or events such as induced abortion, resuscitation, respiratory distress syndrome (RDS), moderate or severe neonatal asphyxia, early foetal death or neonatal or perinatal death must be reported in the eCRF and as an SAE as per Section [12.5.2](#).
- To measure umbilical cord IDeg levels a cord blood sample should be drawn from the umbilical cord (applicable for subjects randomised to IDeg only). The sample should be collected at birth immediately after the umbilical cord has been cut.
- Umbilical cord pH (as part of standard of care).
- Postpartum neonatal plasma glucose and neonatal hypoglycaemia as defined in Section [8.5.16.4](#).
- Treatment given to the infant, e.g. with surfactant, ventilator or continuous positive airway pressure (CPAP).

#### **8.4.3 End of treatment**

The end of treatment visit should take place 28 days after delivery. A treatment completion session must be performed in the IWRS, treatment with trial product must be stopped, and the subject should be switched to a suitable marketed insulin regimen at the discretion of the investigator.

Both the mother and the infant will undergo a physical examination and infant health will be assessed (not applicable in case of fatal outcome) as outlined in Section [12](#).

#### **8.4.4 Premature discontinuation of trial product**

If a pregnant subject prematurely discontinues trial product, the investigator must perform the additional end of treatment visit 90A as soon as possible, Section [8.4.3](#). The additional follow-up contacts P91A and V92A must be performed 7 and 30 days after discontinuation of trial product respectively, Section [8.5.3](#).

The primary reason for premature discontinuation of trial product must be specified in the end of treatment form in the eCRF, and final drug accountability must be performed. A treatment discontinuation session must be made in the IWRS.

Protocol  
 Trial ID: NN1250-4300  
 UTN: U1111-1191-3018  
 EudraCT no.: 2017-000048-17

[figure not shown]
**CONFIDENTIAL**

Date: 17 December 2020  
 Version: 4.0  
 Status: Final  
 Page: 43 of 110

**Novo Nordisk**

Pregnant subjects discontinuing treatment prematurely should hereafter attend all remaining planned visits of the trial. If applicable, the phone contacts should preferably be completed weekly in order to maintain glycaemic control.

For subjects not able or willing to attend all planned site visits, these can be converted to phone contacts. Efforts should be made to ensure collection of the scheduled 9-point profiles as per flowchart Section 2.3 and attendance at the most important key visits, i.e. visit 79 for collection of an HbA1c sample prior to delivery, the delivery visit, the end of treatment visit V90 (except 2-point profile), and the originally scheduled V92 follow-up visit. The key visits to be completed for subjects discontinuing treatment prematurely are summarised in [Figure 8-2](#).

Abbreviations: V2 = pregnancy baseline visit (ultrasound scan), EOT = end of treatment (V90), FU2 = follow-up visit 2 (V92), EOT-A = additional end of treatment (V90A), FU1-A/FU2-A = additional follow-up contacts 1 (P91A) and 2 (V92A), V79 = gestational week 36, D = delivery (V86).

**Figure 8-2 Overview of key visits for subjects discontinuing treatment prematurely in the pregnancy period of the trial.**

#### 8.4.5 Withdrawal from trial

If a subject withdraws consent, the investigator must aim to undertake procedures similar to those for the end of treatment visit as soon as possible. If the subject agrees, the P91 and V92 follow-up contacts must be performed 7 and 30 days after discontinuation of trial product respectively.

The end of trial form must be completed and final drug accountability must be performed even if the subject is not able to come to the trial site. A treatment discontinuation session must be made in the IWRS and the casebook must be signed.

If the subject has already discontinued treatment prematurely and attended the additional end of treatment visit 90A as well as the additional follow-up contacts P91A and V92A prior to withdrawal, the end of treatment visit V90 and follow-up contacts P91 and V92 should not be completed.

The investigator should collect information about the pregnancy, pregnancy outcome and infant health on the paper pregnancy forms as per Section 12.5.

Protocol  
Trial ID: NN1250-4300  
UTN: U1111-1191-3018  
EudraCT no.: 2017-000048-17

~~CONFIDENTIAL~~

Date: 17 December 2020  
Version: 4.0  
Status: Final  
Page: 44 of 110

**Novo Nordisk**

Although a subject is not obliged to give her reason(s) for withdrawing consent, the investigator must make a reasonable effort to ascertain the reason(s), while fully respecting the subject's rights. Where the reasons are obtained, the primary reason for withdrawing consent must be specified in the end of trial form in the eCRF.

## **8.5 Visit procedures and assessments for both non-pregnant and pregnant subjects**

### **8.5.1 Phone contacts**

Throughout the trial (both in the conception and the pregnancy periods of the trial) weekly phone contacts are scheduled according to Sections [2.2](#) and [2.4](#). Phone contacts must be completed in the eCRF and documented in the subject's medical records. A phone contact may be converted to a site visit if preferred.

It must be clearly agreed how each contact is conducted. Even if it is agreed that the subject calls the investigator, it is the responsibility of the investigator that the contact takes place.

#### **Additional phone contacts in the conception period of the trial**

The additional phone contacts P54A-P54G are flexible phone contacts applicable for non-pregnant subjects becoming pregnant in the conception period of the trial only. These phone contacts should be completed as needed to ensure weekly contacts between the last site visit and the scheduled ultrasound scan at visit 55.

#### **Additional phone contacts in the pregnancy period of the trial**

The additional phone contacts P55A-P55C and P56-P58 are flexible phone contacts that should be completed as needed to ensure weekly contacts until visit 59.

The additional phone contacts P83-P85 are flexible phone contacts applicable for pregnant subjects with delivery after GW 40.

### **8.5.2 Fasting visits**

Subject must attend specific visits in a fasting condition as outlined in the flowchart Sections [2.1](#) and [2.3](#) for collection of an FPG blood sample. Fasting is defined as having consumed only water and taken no insulin at least eight hours prior to the visit. Non-antidiabetic medication(s) are to be taken.

If a subject attends a fasting visit in a non-fasting condition, blood sampling should be re-scheduled preferably within the visit window. If blood sampling has already been done before realising the subject was not fasting, only the FPG sample needs to be re-drawn.

Protocol  
 Trial ID: NN1250-4300  
 UTN: U1111-1191-3018  
 EndraCT no.: 2017-000048-17

CONFIDENTIAL

Date: 17 December 2020  
 Version: 4.0  
 Status: Final  
 Page: 45 of 110

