### 5.3 Treatment of subjects

Eligible subjects will be randomised 1:1 in an open-label manner to one of the below treatment regimens:

- IDeg OD + IAsp 2-4 times daily with meals, or
- IDet OD/BID + IAsp 2-4 times daily with meals

Following randomisation, pre-trial insulin treatment must be discontinued and the subject will be switched to randomised treatment. Initiation and doses of trial basal insulin is based on plasma glucose values and are adjusted according to the Insulin Titration Guideline in [Appendix A](#). There is no minimum or maximum daily insulin dose specified. Surveillance of insulin titration will be performed by Novo Nordisk.

End of treatment will be 28 days after delivery for pregnant subjects. For subjects who do not become pregnant in the conception period of the trial, the end of treatment visit (visit 90) will be 7 days after visit 54.

After end of treatment each subject will have a 30 days safety follow-up period consisting of two follow-up contacts (P91 and V92), see Section [8.5.3](#).

The maximum duration of treatment of a single subject will depend on whether the subject is randomised non-pregnant or pregnant as summarised in [Table 5-1](#).

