### 6.2 Inclusion criteria

For an eligible subject, all inclusion criteria must be answered “yes”.

1. Informed consent obtained before any trial-related activities. Trial-related activities are any procedures that are carried out as part of the trial, including activities to determine suitability for the trial.
2. Female, age  $\geq 18$  years at the time of signing informed consent.
3. Diagnosed with type 1 diabetes mellitus  $\geq 1$  year prior to the day of screening.
4. Treated with multiple daily subcutaneous insulin injections or continuous subcutaneous insulin infusion (CSII) or inhaled insulin  $\geq 90$  days prior to the day of screening.
5. The subject is planning to become pregnant within 12 months from randomisation and willing to undertake pre-pregnancy counselling *or* the subject is pregnant with an intrauterine singleton living foetus (gestational week 8 to 13 (+6 days)) without any observed anomalies at randomisation, confirmed by an ultrasound scan.
6. HbA1c at screening  $\leq 8.0\%$  (64 mmol/mol) by central laboratory.
7. Willingness and ability to take folic acid according to local guidelines.

Protocol  
 Trial ID: NN1250-4300  
 UTN: U1111-1191-3018  
 EudraCT no.: 2017-000048-17

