### 8.2 Randomisation

Randomisation should take place no later than 21 days after the screening visit, but must not take place before all screening assessment results are available and reviewed and the subject confirmed eligible. For an eligible subject a randomisation session must be performed in the IWRS where subject will be randomised into one of the two treatment regimens and trial product will be dispensed.

The subject must attend the randomisation visit fasting as defined in Section [8.5.2](#).

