#### **8.5.10 Concomitant medication (diabetes)**

A **concomitant antidiabetic medication** is any diabetes medication other than the trial product(s). At the randomisation visit any pre-trial insulin(s) must be discontinued and stop date(s) recorded in the eCRF.

Protocol  
Trial ID: NN1250-4300  
UTN: U1111-1191-3018  
EudraCT no.: 2017-000048-17

CONFIDENTIAL

Date: 17 December 2020  
Version: 4.0  
Status: Final  
Page: 47 of 110

Novo Nordisk

For subjects randomised non-pregnant this includes diabetes medication taken up to 28 days before screening as well as during the trial, including the screening, conception and/or pregnancy period(s) of the trial and until the end of trial. The information must be recorded in the concomitant antidiabetic medication form in the eCRF.

For subjects randomised pregnant this includes diabetes medication taken at least 28 days before conception as well as during the trial, including the screening and pregnancy periods of the trial and until the end of trial. The information must be recorded in the concomitant antidiabetic medication form in the eCRF.

The information collected for each antidiabetic medication must be recorded in the concomitant antidiabetic medication form in the eCRF. Details include trade name or generic name, indication, route of administration, total daily dose, start date and stop date.

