**Novo Nordisk**

## 17 Statistical considerations

If necessary, a statistical analysis plan (SAP) may be written in addition to the protocol, including a more technical and detailed elaboration of the statistical analyses. The SAP will be finalised before database lock.

The internal Novo Nordisk blinding plan will describe how blinding of the randomised treatments for internal Novo Nordisk personnel will be maintained until the database has been released for statistical analysis. No interim analyses or other analyses of unblinded data will be performed before the database is locked.

Data from all sites will be analysed and reported together.

In statistical analyses where stratification is included, pregnancy status (Pregnant/Non-pregnant) and planned continuous use of CGM (Yes/No) will be based on the actual information. Hence, if subjects by mistake are allocated to a wrong randomisation list, the correct stratification factor will be applied.

In the statistical models explanatory factors will be parameterized as follows:

- Treatment: IDeg, IDet
- Stratification factor: randomised as pregnant and planned continuous use of CGM, randomised as pregnant and no planned continuous use of CGM, randomised as non-pregnant and planned continuous use of CGM, randomised as non-pregnant and no planned continuous use of CGM.
- Region: Europe (Austria, Denmark, Greece, Ireland, Italy, United Kingdom and Serbia), North America (Canada), South America (Argentina and Brazil) and Asia/Oceania (Australia, Israel and Russia).

Two different baselines will be applied; a treatment baseline and a pregnancy baseline. The treatment baseline value will be used in the statistical models and is defined as the latest available measurement at or before randomisation. For all subjects the treatment baseline value hence corresponds to the value obtained at the randomisation visit (visit 2) if available, or at the screening visit (visit 1). If neither of these measurements have been obtained the treatment baseline will be left missing. For subjects randomised pregnant the pregnancy baseline is derived from the treatment baseline, and the two baseline values will be identical, corresponding to the values obtained at visit 2 or visit 1. For subjects randomised non-pregnant and becoming pregnant in the conception period of the trial, the pregnancy baseline corresponds to data from visit 55.

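### Section 8.5.2 defines fasting as no insulin for eight hours with no exception for a running pump, although pump users are eligible and still on their pumps before fasting visit V2: a minor safety wording error of unknown scale

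*Protocol*

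**What the plan says.** Protocol section 8.5.2 defines the fasting condition: "Fasting is defined as having consumed only water and taken no insulin at least eight hours prior to the visit." On what continues, it says only this: "Non-antidiabetic medication(s) are to be taken." Insulin is not among the medicines carried on. If a woman arrives non-fasting, sampling is re-scheduled, and "If blood sampling has already been done before realising the subject was not fasting, only the FPG sample needs to be re-drawn."

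Four other places bear on this:

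- **Eligibility (section 6.2).** Criterion 4 admits women "Treated with multiple daily subcutaneous insulin injections or continuous subcutaneous insulin infusion (CSII) or inhaled insulin" for at least 90 days before screening.
- **V2 (section 8.2).** "The subject must attend the randomisation visit fasting as defined in Section" 8.5.2.
- **End of pre-trial insulin (sections 5.3 and 8.5.10).** "Following randomisation, pre-trial insulin treatment must be discontinued and the subject will be switched to randomised treatment." The second statement reads: "At the randomisation visit any pre-trial insulin(s) must be discontinued and stop date(s) recorded in the" eCRF.
- **Baseline (section 17).** The treatment baseline "is defined as the latest available measurement at or before randomisation", and the same paragraph equates it with the V2 value where there is one.

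**The concern.** A basal injection can be timed more than eight hours before a morning visit and so satisfy the definition. A continuous infusion cannot. For a woman on a pump the text leaves two courses: suspend delivery for eight hours, or count as non-fasting.

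Suspension would leave a woman with type 1 diabetes without any insulin delivery overnight. She might be in gestational week 8 to 13, or about to try to conceive. Protocol section 3.2 itself treats glucose control at exactly these times as essential. The other course puts a site that sensibly keeps the pump running at odds with a mandatory instruction, and section 19.1 asks that deviations be avoided and documented.

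The measurement does not need the strict wording. Section 8.5.17 gives the purpose of FPG as evaluating metabolic control. Later samples in the degludec arm are drawn while a long-acting basal insulin is working (section 3.1).

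**Working it through.** The plan states no figure on this point, so the check is mainly a comparison of texts.

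**1. Is there an exception?** None was found in the protocol or SAP. CSII appears only in the inclusion criterion (Summary and section 6.2). Appendix A section 1 lets the investigator overrule the titration guideline, but that does not reach the fasting definition. Appendix A section 3.1 gives transfer rules for basal doses and does not mention pumps. The central laboratory manual and the consent pages were not available and could contain an exception.

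**2. Is the pump still in use in the eight hours before V2?** Yes. Sections 5.3 and 8.5.10 stop pre-trial insulin at or after randomisation, and randomisation takes place at V2.

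**3. At which visits does the rule meet a pump?** The fasting rows of flowcharts 2.1 and 2.3 give:

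| Woman | Fasting visits | Pre-trial insulin still in use |
|---|---|---|
| Randomised pregnant | V2, V59, V67, V75, V79 (5) | V2 only (1 of 5) |
| Randomised non-pregnant, conceives | V2, V55, V59, V67, V75, V79 (6) | V2 only (1 of 6) |

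After V2 the trial regimens are injections. The missing basal exception still matters a little at the later visits. Appendix A section 2.2 allows a bedtime detemir dose and degludec at any time of day, so a late dose could fall inside eight hours of an early visit.

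**4. What follows from counting as non-fasting?** Only a re-scheduled or re-drawn FPG sample (section 8.5.2). A re-draw while the pump is still in use meets the same rule. The status of a re-draw after the switch is unclear. Section 17 speaks of a measurement at or before randomisation, but it also equates baseline with the V2 value, and section 8.5.4 asks that a requisition refer to the visit to which the sample belongs.

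**5. Scale.** The CSII share is not given. These are illustrations on assumptions:

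- CSII share 10% to 40% of the 214 planned women (section 6.1): 214 × 0.10 = 21.4 and 214 × 0.40 = 85.6, so 21 to 86 women to whom the wording applies.
- A wider assumption of 5% to 50%: 214 × 0.05 = 10.7 and 214 × 0.50 = 107, so 11 to 107.
- If 0% to 10% of the larger count of 85.6 were told to suspend: 0 to 85.6 × 0.10 = 8.6, so 0 to 9 women. The true number may be zero.

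**6. Data.** The primary endpoint is HbA1c, so the sample size and the 0.4% margin test are untouched. FPG is one supportive endpoint, with its baseline as a covariate. SAP section 5.4.1.1 excludes a woman from that analysis only if baseline FPG is missing, and nothing voids a sample drawn with a pump running.

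**7. Timing.** Protocol version 4.0 is dated 17 December 2020 and the SAP 27 January 2021: 14 + 27 = 41 days later. SAP section 6.3.1.1 already counts 188 women in FAS_pregnant against a target of 178 (protocol section 17.1), a surplus of 10. Most V2 visits are therefore probably past.

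**The case against.** The strongest reply is that the literal reading is not the natural one. Elsewhere the protocol speaks of doses being taken (Table 9-2 footnote; Appendix A sections 3.2 and 4), and section 8.5.14 asks for glucose readings before insulin injection. On that usage, section 8.5.2 bars a dose, not insulin that is still acting; otherwise every later degludec sample would fail. The section describes a sampling condition and never tells anyone to stop a pump. Section 22 makes a qualified physician responsible for trial-related medical decisions.

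Much of this stands. Most investigators would probably read the sentence as excluding a bolus dose. But a pump delivers doses continuously, so the dose reading does not settle the case, and the only medicines told to continue are non-antidiabetic. Safe care should not depend on sites reading past a mandatory definition.

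A second reply concerns the remedy. Simply telling women to continue usual basal insulin would go too far. At every fasting visit it would allow a morning basal injection before the draw. Twice-daily dosing exists only in the detemir arm, so this could affect FPG differently by arm. That objection is correct, and the wording under the fix is narrower for this reason.

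Third, little may be left to correct at V2. That also stands.

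**Conclusion.** The wording gap is certain on the text seen; its consequences are not. It is a minor safety wording error of unknown scale and worth correcting because one amended definition removes it. The count of 21 to 86 women rests wholly on an assumed CSII share and measures exposure to the wording.

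A reader might infer more, and the documents do not support it:

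- **That women were or will be left without insulin.** Nothing shows that any site reads the sentence literally.
- **That pump users lose their baseline FPG, or that a re-draw after the switch can never serve as baseline.** Sections 8.5.4 and 17 leave that open.
- **That the rule will meet pumps again after women stop trial product.** Section 5.4 allows a switch to a suitable marketed product, but no passage says this would be CSII, so no count can be supported.
- **That the efficacy conclusion is at risk.** HbA1c, power and the non-inferiority test are unaffected. At most there is slight noise in the baseline covariate of one supportive endpoint.

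**What to change.** Replace the definition in section 8.5.2 with wording such as:

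*Fasting means that, for at least eight hours before the visit, the subject has had only water and no bolus insulin, and has taken no morning basal injection before the sample. A CSII basal rate must not be suspended. An evening or bedtime basal dose is taken as usual. Insulin needed to correct hyperglycaemia must not be withheld; re-schedule the FPG sample instead.*

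Add that a morning basal injection is given after the FPG draw in both arms. This keeps the sampling condition the same for degludec and detemir.

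The cost is a short text change and some heterogeneity in baseline FPG by prior regimen. The SAP need not change. If randomisation has closed, send the text to sites as a clarification for the remaining fasting visits.

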**Novo Nordisk**

### 8.5.3 Follow-up period

There are two follow-up contacts after end of treatment, P91 and V92.

The first follow-up contact (P91) is a phone contact and must take place 7 days after end of treatment. At this visit information about antidiabetic medication and all AEs including hypoglycaemic episodes in the period from end of treatment visit V90 to P91 is collected.

The second follow-up contact (V92) is a site visit and is considered the end of trial visit. This site visit must take place 30 days after end of treatment visit V90. Information about antidiabetic medication and all AEs including hypoglycaemic episodes in the period between the two follow-up contacts is collected. Status on infant health (if applicable) will be collected for the period from end of treatment visit V90 until V92.

